9.6.1.2.9 Self-reported nicotine and tobacco containing product use

For self-reported daily cigarette consumption and/or IQOS use (self-reported nicotine and tobacco containing product use) see Section 9.5 "Extent of Exposure (Product Consumption)".

9.6.1.3 Supportive/Sensitivity Analyses

If deemed appropriate, selected endpoint analyses will additionally be performed for the FAS.

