Missing data for self-reported daily use will not be imputed and we will assume that the derived average monthly use from non-missing data is representative of the actual usage. For each analysis period (Week 1 or Overall), if more than 50% of product use data is not available then the subject will be grouped into the 'Others' product use arm. Therefore, it is possible that a subject is not considered for statistical modelling as it is grouped into 'Others' for Week 1 (3 out of 7 days of product use data only) but available for analysis for the entire study period if more than 50% of product use data was eventually collected throughout the study. A subject may have switched product use groups throughout the study and the total number of subjects in an arm may fluctuate over time depending on the actual product use.

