8.1 Full Analysis Set

The Full Analysis Set (FAS) consists of all randomized subjects who have at least one postrandomization product (cigarette or IQOS) use experience if randomized to IQOS, IQOS-2 or cigarette arm, and who have at least one valid non-safety assessment after randomization. All subjects in the SA arm who fulfil these requirements, except the product use experience, are part of this set as well. The FAS will be analyzed by randomized study arm.

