8.3 As Exposed Exercise Compliant Set

The As Exposed Exercise Compliant Set (AEECS) consists of all randomized subjects who have at least one valid non-safety assessment after randomization, specifically we have

- post-randomization product (cigarette or IQOS) use experience if randomized to IQOS, • IQOS-2 or cigarette arm or
- no product use if randomized to the SA arm,

and who attended at least 34 of 38 (~90%) of the exercise training sessions except the subjects in IQOS-2 arm. Subjects in the IQOS-2 will be analyzed as exposed as they did not participate in the training. The AEECS will be analyzed by actual exposure (product use exposure, actual study arm).

Due to technical issues with the bike training equipment during the study, these rules are used to determine if a subject completed a training session for the purposes of defining the AEECS analysis set in addition to information regarding whether a training visit was done or not. We define a training session to be completed if a minimum of 20 or more minutes of exercise was done. If the training time is unknown then the session is considered to be not done. These checks from the protocol deviation dataset will be done regardless of whether data from the exercise training is available or not.

For a training session to be considered as not done from the protocol deviations (PD) dataset, the PD description will be checked for the following,

- "Bike training was not done" •
- "Bike training was partially completed for less than 20 min ..."
- "Bike training was partially completed for unknown number of minutes ..."

A bike training session is considered as complete if the following description for bike training is provided in the PD dataset,

- "Bike training was completed..."
- "Bike training was partially completed for at least 20 min..." •

In the case where there are inconsistencies between the PD dataset and bike training data, ie, for example bike training was marked as complete but the PD descriptions says otherwise, the PD rules will be used to determine completion of a bike training session.

Confidentiality Statement

Philip Morris Products SA.	Statistical Analysis Plan	Confidential
P1-EXC-01-EU	Final 2.0	Page 32 of 71
Related to PMI-RRP-WKI-112487		

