9.1.1 Stratified Presentation

Stratification criteria for the evaluation are:

- Randomized study arm Cigarette, IQOS-1, smoking abstinence (SA), IQOS-2) randomized arm.
- Product use (actual arm) i.e. actual product use exposure categorized based on self-reporting and biochemical verification according to Section 5.5.1 "Product Use Pattern":

Confidentiality Statement

Data and information contained in this document are considered to constitute trade secrets and confidential commercial information, and the legal protections provided to such trade secrets and confidential information are hereby claimed under the provisions of applicable law. No part of this document may be publicly disclosed without the written consent of Philip Morris Products S.A

Philip Morris Products SA.	Statistical Analysis Plan	Confidential
P1-EXC-01-EU	Final 2.0	Page 34 of 71
Related to PMI-RRP-WKI-112487		SAP_P1-EXC-01-EU

- o Cigarette,
- o IQOS-1,
- Smoking Abstinence (SA),
- IQOS-2,
- Dual users considered for IQOS-1 (Dual-1),
- Dual users considered for IQOS-2 (Dual-2),
- Cigarette consumption at V1 (10 to 19 cigarettes, more than 19 cigarettes per day)
- Sex (male, female)
- Age (<50, ≥ 50 years i.e. $21 \le Age < 50$ and $50 \le Age \le 65$])

The main stratification criterion for the evaluation is the actual product exposure, whereas data will be listed by randomization arm.

Further stratification by cigarette consumption and sex will be done for the analysis of VO_2max and exercise capacity and where explicitly defined. Further stratification by age and BMI will be done only where explicitly defined (e.g. for demographic data).

The AEECS, AEBECS and the Safety Set will be analyzed by actual study arm (product use exposure). The FAS will be analyzed by randomized study arm.

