9.6.1 Endpoint Analyses

The following non-safety endpoints will be analyzed using the AEECS considering the actual study arm (i.e. product use exposure). The following sections describe the statistical models used in analyzing the endpoints as well as descriptive statistics used for summarizing the data.

In general, for model based analysis all visit data will be used and analyzed within the same model.

- 9.6.1.1 Statistical Analysis of Endpoints
- 9.6.1.1.1 To evaluate changes in VO₂max in subjects switching to IQOS (with and without training), continuing to smoke cigarettes (with training) and being smoking abstinent

A linear mixed effects model will be used to estimate the difference in VO₂max between each arm (SA arm, IQOS-1+IQOS-2 combined arm, Dual-1+Dual-2 arm) versus cigarette arm one week after randomization (V4) and after completion (SA arm, IQOS-1 arm, IQOS-2 arm, Dual-1 arm) of the 12-week training program (V43). The degrees of freedom will be adjusted by using Kenward Roger (KR) method and the Saitterthwaite method will be used in case of convergence issues. Both V4 and V43 data will be used together in the same model. At V4, both IQOS-1 and IQOS-2 will be combined into a single IQOS group as these subjects did not attend any exercise training.

The dependent variable will be the VO₂max change from baseline with baseline VO₂max, arm, visit, sex, age and visit*arm as *fixed* covariates and subject fitted as a random effect. In addition, the following *exploratory* covariates BMI, RPC, COHb levels at each visit, cigarette consumption at V1, IPAQ score at V1, average step count 2 weeks prior to visit, self-reported daily cigarette consumption (from randomization until each visit), cigarette smoking 30-60 minutes before test for subjects in cigarette arm and IQOS use 30-60 minutes before test for subjects in IQOS arm will be assessed for adequacy in the model using a step-wise (backward) approach through the following algorithm.

Data and information contained in this document are considered to constitute trade secrets and confidential commercial information, and the legal protections provided to such trade secrets and confidential information are hereby claimed under the provisions of applicable law. No part of this document may be publicly disclosed without the written consent of Philip Morris Products S.A

Philip Morris Products SA.	Statistical Analysis Plan	Confidential
P1-EXC-01-EU	Final 2.0	Page 40 of 71
Related to PMI-RRP-WKI-112487		

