15.2 Tables		
Table 15.2.1.1: Summary of Subject Disposition - Screened Subjects		X
Table 15.2.1.2: Summary of Reasons for Discontinuation – Subjects in FAS, AEECS and AEBECS		
Table 15.2.1.3: Analysis Sets and Summary of Reason for Exclusion from		
Analysis Sets		
Table 15.2.1.4: Number of Subjects in the Analysis Sets by Arm – AEECS,		
AEBECS, Full Analysis Set		
Table 15.2.1.3.1: Demographic and Baseline Characteristics – AEECS	Х	Х
Table 15.2.1.3.2: Demographic and Baseline Characteristics – AEBECS		
Table 15.2.1.3.3: Demographic and Baseline Characteristics – Full Analysis Set		
Table 15.2.1.4.1: Summary of Product Use (Week 1) – AEECS	Х	X
Table 15.2.1.4.2: Summary of Product Use (Overall) – AEECS		
Table 15.2.1.4.3: Summary of Product Use (Week 1) – AEBECS		
Table 15.2.1.4.4: Summary of Product Use (Overall) – AEBECS		
Table 15.2.1.4.5: Summary of Product Use (Overall) – Full Analysis Set		
Table 15.2.1.5: Summary of Product Preference – AEECS		
Table 15.2.1.6.1: Summary of Protocol Deviations – Safety Set		
Table 15.2.1.7.1: Summary of Lifestyle Questionnaire - AEECS		
Table 15.2.1.8: Summary of IPAQ Questionnaire – AEECS		
Table 15.2.2.1.1: Analysis of VO2max Change from Baseline (Acute Effect, V4) – AEECS	х	x
Table 15.2.2.1.2: Analysis of VO2max Change from Baseline (Training Effect, V43) – AEECS	х	X
Table 15.2.2.1.3: Regression Coefficients for Analysis of VO2max Change from Baseline – AEECS	х	Х
Table 15.2.2.1.4: Variable Selection in Analysis of VO2max Change from Baseline – AEECS	х	Х
Table 15.2.2.1.5: Descriptive Statistics of VO2max Change from Baseline - AEECS	х	Х
Table 15.2.2.1.6: Analysis of VO2max Change from Baseline (Acute Effect, V4) – Full Analysis Set		
Table 15.2.2.1.7: Analysis of VO2max Change from Baseline (Training Effect, V43) – Full Analysis Set		

Confidentiality Statement

Philip Morris Products SA.	Statistical Analysis Plan	Confidential
P1-EXC-01-EU	Pending Approval 0.1, CURRENT, IN PROGRESS	Page 66 of 71
Related to PMI-RRP-WKI-112487		DD SME01 810208 SAD D1

Table 15.2.2.1.8: Regression Coefficients for Analysis of VO2max Change from		
Baseline – Full Analysis Set		
Table 15.2.2.1.9: Variable Selection in Analysis of VO2max Change from		
Baseline – Full Analysis Set		
Table 15.2.2.1.10: Descriptive Statistics of VO2max Change from Baseline – Full Analysis Set		
Table 15.2.2.1.11: Analysis of VO2max Change from Baseline (Acute Effect, V4)		
– AEBECS		

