Table 15.2.2.4.4.1: Regression Coefficients for Analysis of Heart Rate – AEECS	
Table 15.2.2.4.5.1: Regression Coefficients for Analysis of Oxygen Uptake –	
AEECS	

Confidentiality Statement

Philip Morris Products SA.	Statistical Analysis Plan	Confidential
P1-EXC-01-EU	Pending Approval 0.1, CURRENT, IN PROGRESS	Page 68 of 71
Related to PMI-RRP-WKI-112487		DD SME01 810208 SAD D1

Table 15.2.2.4.6.1: Descriptive Statistics of Physiological and Respiratory	
Parameters by Workload - AEECS	
Table 15.2.2.4.7.1: Descriptive Statistics of RPC (continuous) by Sex – AEECS	
Table 15.2.2.5.1.: Analysis of the Average Step Count by Month – AEECS	X
Table 15.2.2.5.2.: Regression Coefficients for Analysis of Average Step Count	
by Month – AEECS	
Table 15.2.2.5.3: Descriptive Statistics of mHealth variables - AEECS	Х
Table 15.2.2.6.1: Analysis of the Changes in Biological Health Markers fromBaseline at V14, V28 and V43 – AEECS	
Table 15.2.2.6.2: Regression Coefficients for Analysis of Changes in Biological	
Health Markers from Baseline – AEECS	
Table 15.2.2.6.3: Descriptive Statistics of Biological Health Markers - AEECS	
Table 15.2.2.6.4: Analysis of the Changes in Biological Health Markers from	
Baseline at V14, V28 and V43 – AEBECS	
Table 15.2.2.6.5: Regression Coefficients for Analysis of Changes in Biological	
Health Markers from Baseline – AEBECS	
Table 15.2.2.6.6: Descriptive Statistics of Biological Health Markers - AEBECS	
Table 15.2.2.7.1: Analysis of the Changes in Body Fat and Waist Circumference	
from Baseline (Acute Effect, V4) – AEECS	
Table 15.2.2.7.2: Analysis of the Changes in Body Fat and Waist Circumference	
from Baseline (Exercise Effect, V43) – AEECS	
Table 15.2.2.7.3: Regression Coefficients for Analysis of the Changes in Body	
Fat and Waist Circumference from Baseline– AEECS	
Table 15.2.2.7.4: Summary of Body Fat and Waist Circumference by ProductUse Category - AEECS	
Table 15.2.2.7.5: Analysis of the Changes in Body Weight from Baseline byMonth – AEECS	
Table 15.2.2.7.6: Regression Coefficients for Analysis of the Changes in Body	
Weight from Baseline– AEECS	
Table 15.2.2.7.7: Summary of Body Weight by Product Use Category – AEECS	
Table 15.2.2.8.1: Descriptive Statistics for Exhaled CO – AEECS	
Table 15.2.2.8.2: Descriptive Statistics for Biomarkers of Exposure - AEECS	Х
Table 15.2.2.8.3: Descriptive Statistics for Exhaled CO – AEBECS	
Table 15.2.2.8.4: Descriptive Statistics for Biomarkers of Exposure - AEBECS	

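### The only analysis by randomised arm is conditional in SAP 9.6.1.3, against the SAP's own table list for VO2max and exercise capacity, and is planned for none of the other five modelled objectives

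*SAP*

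**What the plan says.** Subjects are randomised 5:5:5:3 to IQOS-1, cigarette, smoking abstinence (SA) and IQOS-2 (SAP 4.1). The analysis then follows use and not allocation.

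- SAP 9.6.1: "The following non-safety endpoints will be analyzed using the AEECS considering the actual study arm (i.e. product use exposure").
- SAP 9.1.1: "The main stratification criterion for the evaluation is the actual product exposure, whereas data will be listed by randomization arm".
- SAP 5.5.1 sets the groups from diary data and notes that "A subject may have switched product use groups throughout the study".
- SAP 8.3 adds a second filter for the three training arms: the AEECS keeps subjects who meet the product-use conditions "and who attended at least 34 of 38 (~90%) of the exercise training sessions".
- SAP 8.1 defines the one exception: "The FAS will be analyzed by randomized study arm".
- SAP 9.6.1.3 governs when that exception is used: "If deemed appropriate, selected endpoint analyses will additionally be performed for the FAS".

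Section 13.2 nevertheless lists specific FAS tables, for example "Analysis of VO2max Change from Baseline (Acute Effect, V4) – Full Analysis Set" (Table 15.2.2.1.6), with no condition attached. For other objectives it lists none. For instance, "Analysis of the Changes in Biological Health Markers fromBaseline at V14, V28 and V43" appears for the AEECS and for the biochemically verified subset (AEBECS), but not for the FAS.

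**The concern.** Whether a subject stays exclusively on IQOS, uses both products, or relapses from abstinence is decided after randomisation. It is plausibly linked to motivation and effort, which also affect training response and fitness. Attendance at training is closer still to the outcome. A difference between as-exposed groups therefore mixes any product effect with a difference between people who adhere and people who do not.

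The sponsor treats this as a live possibility. SAP 9.4 expects dual use and relapse, and SAP 9.6.2.1 models whether product preference drives compliance. The usual safeguard is an estimate by randomised arm beside the as-exposed one. Here the SAP text makes that estimate conditional, and the table list omits it for most modelled endpoints. For those endpoints the reader of the report would have no comparison protected by randomisation.

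Section 9.6.1.3 also sets no date for its decision. SAP Table 1 blinds the statisticians only to post-randomisation VO2max and exercise capacity results, and only until database lock. Results for the other objectives are not on that list.

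**Working it through.** **1. Where the FAS appears.** Count of the endpoint tables (15.2.2.x) in SAP 13.2 by analysis set:

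| Objective | AEECS | AEBECS | FAS |
|---|---|---|---|
| 1 VO2max | 5 | 5 | 5 (15.2.2.1.6–10) |
| 2 Exercise capacity | 10 | 5 | 5 (15.2.2.2.6–10) |
| 3 Training intensity | 4 | 0 | 0 |
| 4 Physiology, exertion | 12 | 0 | 0 |
| 5 Physical activity | 3 | 0 | 0 |
| 7 Health markers | 3 | 3 | 0 |
| 8 Weight, fat, waist | 7 | 0 | 0 |
| 9 Exposure | 2 | 2 | 0 |
| Total (71) | 46 | 15 | 10 |

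Objectives 3, 4, 5, 7 and 8 have mixed-model comparisons between groups in SAP 9.6.1.1.3 to 9.6.1.1.7. Objective 9 is descriptive only. Apart from the ten tables above, the FAS appears only in disposition, demographic and product-use tables.

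**2. The plan's own precision figure, as a yardstick.** Inputs from SAP 6: SD 14 mL/kg/min, 20 evaluable per arm, 90% probability.

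- Expected half-width: t(0.975; 38) × 14 × √(2/20) = 2.024 × 4.427 = 8.96.
- 90% bound: 8.96 × √(49.51/38) = 8.96 × 1.141 = 10.23.

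The plan states about 10.3, so the figure reproduces and this point does not affect it. With all 25 per arm contributing, the same formula gives 8.97.

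**3. Illustrative size of the selection bias.** None of these inputs is in the documents; all are assumptions. There is no product effect. A latent trait has correlation 0.7 with adherence and r = 0.2 to 0.4 with the outcome change. Of IQOS subjects, 30–40% are dual users; of SA subjects, 40–60% relapse. There are 25 subjects per arm.

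If a fraction q of an arm is retained by adherence, the mean outcome of those retained is shifted by 0.7 × r × m(q) SD, where m(q) = φ(z_q)/q. This gives m(0.7) = 0.497, m(0.6) = 0.644 and m(0.4) = 0.966.

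Relapsers excluded (cigarette arm unselected):

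- IQOS minus cigarette: 0.7 × 0.2 × 0.497 = 0.07 up to 0.7 × 0.4 × 0.644 = 0.18 SD.
- SA minus cigarette: 0.7 × 0.2 × 0.644 = 0.09 up to 0.7 × 0.4 × 0.966 = 0.27 SD.

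Relapsers moved into Cigarette. At 40% relapse, 10 of the 35 subjects in that group are relapsers, who lower its mean by 0.7r × 0.966 × 10/35 = 0.7r × 0.276. At 60%, 15 of 40 lower it by 0.7r × 0.644 × 15/40 = 0.7r × 0.241.

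- IQOS minus cigarette: 0.14 × (0.497 + 0.276) = 0.11 up to 0.28 × (0.644 + 0.241) = 0.25 SD.
- SA minus cigarette: 0.14 × (0.644 + 0.276) = 0.13 up to 0.28 × (0.966 + 0.241) = 0.34 SD.

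Simulation of the same set-up agrees: 0.06–0.18 and 0.09–0.27 SD with exclusion, 0.11–0.25 and 0.13–0.34 SD with regrouping. The nominal 95% interval excluded zero in 5–10% of trials with exclusion and about 7–15% with regrouping. By randomised arm, bias was about 0 and exclusion about 5%.

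**The case against.** **The FAS tables are already planned.** This is right for VO2max and exercise capacity. SAP section 1 says the plan lists the study's tables, is finalised before database lock, and requires changes to be described in the report. A reader might infer from 9.6.1.3 that the by-arm result for these two endpoints can be dropped freely, or chosen once the data are known. The documents do not support that: dropping a listed table would be a documented departure. What stands is that two parts of the SAP disagree.

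**No topline flag means little.** Agreed. The flag marks what goes into the topline package (SAP 10.3). Its absence does not mean that a table goes unreported.

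**The study is descriptive and the protocol names the AEECS as main set.** Both are true (SAP 3.3.1, protocol 12.4). No hypothesis is tested, so the rates at which intervals exclude zero should not be read as a type I error. But the plan does report between-arm estimates with 95% intervals, and bias in an estimate does not depend on a test. Keeping the AEECS as main set is compatible with showing the by-arm result beside it.

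**The bias figures depend on how relapsers are handled.** This stands. SAP 8.3 can be read as excluding SA subjects with any product use, and the categorisation rule is in a figure not shown in the copy reviewed. That is why both versions are given. The calculation also omits the attendance filter and the planned covariates.

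**Covariates adjust for actual use.** They do not settle it. The candidates in SAP 9.6.1.1.1 include COHb at each visit and daily cigarettes since randomisation. These do not measure motivation, and they may absorb part of the product effect.

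**Conclusion.** The point holds in two parts. For VO2max and exercise capacity, section 9.6.1.3 is conditional while section 13.2 is not, and the two must be reconciled. For the other modelled endpoints (objectives 3, 4, 5, 7 and 8), following the plan leaves every between-arm contrast without an estimate by randomised arm.

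The actual bias cannot be derived from the documents. Under the stated assumptions it is about 0.06–0.25 SD (IQOS minus cigarette) and 0.09–0.34 SD (SA minus cigarette), in each case favouring IQOS or abstinence. For scale, at the plan's VO2max SD of 14, the upper ends are 0.25 × 14 = 3.5 and 0.34 × 14 = 4.8 mL/kg/min. Both are well inside the planned half-width of 10.3, so this is a moderate distortion and not one that swamps the design. The stronger claim, that the randomised arms are never compared in this trial, is not supported.

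The FAS is itself not strictly all randomised subjects. It needs one valid post-randomisation assessment and, outside SA, one product use. It is still far closer to the randomised comparison than the AEECS.

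**What to change.** Replace SAP 9.6.1.3 with:

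> The between-arm contrasts for VO2max, exercise capacity, training intensity (three training arms only), blood composition and respiratory parameters, step count, biological health markers, body weight, body fat and waist circumference will also be estimated in the FAS by randomised arm (IQOS-1 and SA versus cigarette, SA versus IQOS-1 and, except for training intensity, IQOS-1 versus IQOS-2; IQOS arms pooled at V4), using the same mixed model with baseline value, age, sex and V1 cigarette consumption as the only covariates besides arm, visit and visit*arm, and reported beside the AEECS result.

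Then align section 13.2:

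- Add the matching FAS tables.
- Drop the FAS variable-selection Tables 15.2.2.1.9 and 15.2.2.2.9, or limit them to baseline covariates.
- Preferably flag 15.2.2.1.6–7 and 15.2.2.2.6–7 as topline.

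Lactate and the VO2 and heart-rate curves are left out because SAP 9.6.1.1.4 plans no between-arm contrast for them. For training intensity the SAP's baseline is V5, about 15 days after randomisation, so that contrast describes change over the training programme and not from randomisation.

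The AEECS stays the main set. The cost is SAP wording, some extra tables and programming, and a by-arm estimate diluted by non-adherence. Because the analysis set and the covariates both differ, a gap between the two results could not be attributed to selection alone, and the report should say so.

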9.6.2 Exploratory Analyses

9.6.2.1 Effect of subject preference on compliance

To explore if a subject's preference has any influence on the compliance of subjects to product use, a log-linear model will be used to estimate the dependence of subject compliance based on randomized arm and preference.

For these subjects, the number of subjects who were compliant (actual arm = randomized arm) and not compliant will be tabulated and used as the response (1=Compliant, 0=Not Compliant). The SAS procedure CATMOD will be used to analyze this data and the sample code is as provided below.

```
proc catmod data=_data;
    response 1 0;
    weight Count;
    model Compliance=Preference|Randomized_Arm / freq prob;
    title2 'Saturated Model';
```

run;

A contingency table showing the compliance vs whether a subject was randomized to preferred group will be presented as well.

9.6.2.2 To evaluate changes in VO₂max in subjects switching to IQOS (with and without training), continuing to smoke cigarettes (with training) and being smoking abstinent based on AEBECS

The impact of biochemical verification of subjects' smoking status (Section 8.4) for VO_2max will be assessed using the same approach as the analysis described in Section 9.6.1.1.1 except that we will use the AEBECS analysis set instead of AEECS.

Descriptive statistics for this analysis set will be presented as well using the same method as described in Section 9.6.1.2.1.

Data and information contained in this document are considered to constitute trade secrets and confidential commercial information, and the legal protections provided to such trade secrets and confidential information are hereby claimed under the provisions of applicable law. No part of this document may be publicly disclosed without the written consent of Philip Morris Products S.A

Philip Morris Products SA.	Statistical Analysis Plan	Confidential
P1-EXC-01-EU	Final 2.0	Page 52 of 71
Related to PMI-RRP-WKI-112487		

9.6.2.3 To evaluate changes in exercise capacity in subjects switching to IQOS (with and without training), continuing to smoke cigarettes and being smoking abstinent - AEBECS

The impact of biochemical verification of subjects' smoking status (Section 8.4) for exercise capacity will be assessed using the same approach as the analysis described in Section 9.6.1.1.2 except that we will use the AEBECS analysis set instead of AEECS.

Descriptive statistics for this analysis set will be presented as well using the same method as described Section 9.6.1.2.2.

9.6.2.4 To describe changes in biological health markers in subjects switching to IQOS (with and without training), continuing to smoke cigarettes (with training) and being smoking abstinent (with training)

The impact of biochemical verification of subjects' smoking status (Section 8.4) for biological health markers will be assessed using the same approach as the analysis described in Section 9.6.1.1.6 except that we will use the AEBECS analysis set instead of AEECS.

Descriptive statistics for this analysis set will be presented as well using the same method as described Section 9.6.1.2.6.

9.6.2.5 To describe changes in levels of exposure to CO, nitrosamines and acrylonitrile in subjects switching to IQOS (with and without training), continuing to smoke cigarettes (with training) and being smoking abstinent (with training)

The impact of biochemical verification of subjects' smoking status (Section 8.4) for levels of exposure to CO, nitrosamines and acrylonitrile will be assessed using descriptive statistics for this analysis set as described Section 9.6.1.2.8.

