4 INVESTIGATIONAL PLAN

4.1 Study Design

This is a randomized, controlled, open-label, 4-arm parallel group study with stratification by daily cigarette consumption over the past 12 months prior to V1 as reported during V1 (i.e. 10 to 19 cigarettes or >19 cigarettes per day) and sex (Figure 1).

A sufficient number of healthy adult smokers will be screened and enrolled after checking that all eligibility criteria have been met, in order to reach 90 randomized subjects.

Smokers will be randomized as follows with a 5:5:5:3 ratio according to strata:

- **1.** switch to IQOS use + participation in training program: IQOS-1 arm, 25 subjects
- **2.** continue cigarette smoking + participation in training program: Cigarette arm, 25 subjects
- **3.** smoking abstinence + participation in training program: SA arm, 25 subjects
- **4.** switch to IQOS use only: IQOS-2 arm, 15 subjects

When 90 randomized subjects are reached, further enrollment will be stopped. Subjects already enrolled in the study will still be eligible for randomization. From randomization, subjects will be instructed to use their allocated product or stay smoking abstinent until the end of the study. Drop-outs will not be replaced.

Acute effect on VO2max and exercise capacity of switching to IQOS will be assessed one week after randomization before initiating the training program, and the combined effect of switching and exercise training will be assessed one week after completion of the 12-week training program.

Figure 1 Study Design

Confidentiality Statement

Philip Morris Products SA.	Statistical Analysis Plan	Confidential
P1-EXC-01-EU	Final 2.0	Page 14 of 71
Related to PMI-RRP-WKI-112487		SAP P1-EXC-01-EU

Subjects will have serial visits at the investigational site as follows:

Screening, V1 (within 28 days prior to V2): No study-specific procedures will be performed before the Informed Consent Form (ICF) has been signed. The subject will also be invited to participate in a sub-study on perception of health and functioning and will sign a separate optional section of the ICF for this part of the study. Subjects will be invited to sign a separate optional consent form for collection of samples for biobanking.

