4.3 Product Allocation and Blinding

4.3.1 Method of Assigning Subjects to Sequence/Product Arms

Randomization will be done through the at any time during the baseline visit. Subjects will be informed about their study arm allocation at the end of V3. Subjects will be randomized in one of the four study arms:

- Cigarette arm with training program
- IQOS-1 arm with training program
- SA arm with training program •
- IQOS-2 arm without training

in a 5:5:5:3 ratio using a stratified randomization based on daily cigarette consumption over the 12 months prior to V1 (10-19 cigarettes/day vs. >19 cigarettes/day), and sex. All subjects will be instructed to adhere to their assigned product/regimen until they complete the study.

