5.3.2 Product Preference

On V3, the following question will be asked to all subjects:

"Which product would you prefer to be randomized to?"

- IQOS
- Cigarette
- Smoking abstinence
- No preference

Confidentiality Statement

Philip Morris Products SA.	Statistical Analysis Plan	Confidential
P1-EXC-01-EU	Final 2.0	Page 25 of 71
Related to PMI-RRP-WKI-112487		SAP_P1-EXC-01-EU

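### The saturated 16-cell preference-by-arm model of compliance (SAP 9.6.2.1) is too sparse for usable standard errors or tests, and its code is not the log-linear model that the text names

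*SAP*

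**What the plan says.** SAP 9.6.2.1 states that "a log-linear model will be used to estimate the dependence of subject compliance based on randomized arm and preference". Compliance is binary: "the number of subjects who were compliant (actual arm = randomized arm) and not compliant will be tabulated". The sample code is PROC CATMOD with `response 1 0`, `weight Count` and the full factorial, "model Compliance=Preference|Randomized_Arm / freq prob", under the heading "title2 'Saturated Model". A contingency table of compliance against randomisation to the preferred group is planned as well.

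Preference comes from one question at V3, "Which product would you prefer to be randomized to" (SAP 5.3.2), with four answers: IQOS, cigarette, smoking abstinence, no preference. There are four arms, allocated "in a 5:5:5:3 ratio using a stratified randomization based on daily cigarette consumption" and sex (SAP 4.3.1). Recruitment runs "in order to reach 90 randomized subjects", and the smallest arm is "switch to IQOS use only: IQOS-2 arm, 15 subjects" (SAP 4.1).

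Section 9.6.2.1 does not name its analysis set. It does not say whether actual arm means the Week 1 or the Overall product-use category of SAP 5.5.1. It gives no rule for sparse or empty cells and no fallback model.

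**The concern.** There are two problems. First, text and code describe different models. A log-linear model works on the log scale of counts, whereas `response 1 0` makes the response function a cell proportion and models it linearly. A programmer cannot satisfy both.

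Second, a saturated model in 16 cells leans on every cell separately. Weighted least squares needs an estimated variance for each cell proportion, and that estimate is zero when all or none of the cell's subjects comply. With about five subjects per cell this will be common. The model would then give no usable standard errors or tests, and a replacement would have to be chosen after the data have been seen.

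**Working it through.** **Planned numbers.** 20 per training arm with 20% dropout: 20 / (1 − 0.20) = 25. Total: 3 × 25 + 15 = 90. The 5:5:5:3 split of 90 gives 90 × 5/18 = 25 and 90 × 3/18 = 15. This matches SAP 4.1 and 6.

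**Cell sizes.** 4 preferences × 4 arms = 16 cells. Mean 90/16 = 5.6; 25/4 = 6.25 in the larger arms; 15/4 = 3.75 in IQOS-2.

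**Where the fit breaks.** The weights come from V = diag{p(1 − p)/n}. One cell with p = 0 or 1 puts a zero on the diagonal, so a 16-cell V has rank 15 and cannot be inverted.

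**Chance for one cell.** With n subjects and compliance c, the chance that all or none comply is cⁿ + (1 − c)ⁿ. At c = 0.8 this is 0.262 + 0.000 = 0.26 for n = 6, and 0.410 + 0.002 = 0.41 for n = 4.

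**Most favourable layout.** Suppose preferences are spread as evenly as possible in every arm: nine cells of 6, three of 7, three of 4 and one of 3 (54 + 21 + 12 + 3 = 90). At c = 0.5 the chance that no cell is degenerate is 0.96875⁹ × 0.984375³ × 0.875³ × 0.75 = 0.360, so at least one is degenerate with probability 64%.

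**Random preferences.** 20,000 simulated tables per scenario, with multinomial preferences within arms of 25/25/25/15 and binomial compliance. All rates are assumptions, because the documents give none. Entries are the probability of at least one 0%, 100% or empty cell. Shares are in the order IQOS / cigarette / abstinence / none.

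| Preference shares (%) | c = 50% | 60% | 70% | 80% | 90% | Any empty cell |
|---|---|---|---|---|---|---|
| Fixed, as even as possible | 64% | 75% | 93% | 99.7% | about 100% | 0 |
| 25/25/25/25 | 90.4% | 93.1% | 98.3% | 99.9% | about 100% | 6% |
| 40/20/20/20 | 95.9% | 97.2% | 99.2% | about 100% | about 100% | 13–14% |
| 50/20/10/20 | 99.6% | 99.7% | 99.9% | about 100% | about 100% | 42–43% |
| 60/10/10/20 | about 100% | about 100% | about 100% | about 100% | about 100% | 62–63% |

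Check on the empty cells with equal shares: the expected number is 4 × 0.75¹⁵ + 12 × 0.75²⁵ = 0.053 + 0.009 = 0.062, in line with the simulated 0.06.

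With compliance differing by arm (IQOS arms 70%, cigarette 95%, abstinence 50%) the probability is 99.98% or more, and 5 to 7 zero-variance cells are expected. With 20/20/20/15 subjects it is at least 96.4% in every scenario.

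**If the AEECS were the set.** SAP 8.3 admits smoking abstinence (SA) subjects only if they used no product. Their actual arm would then nearly always equal their randomised arm, so all four SA cells would be at or near 100% compliance, or empty, by construction.

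**The case against.** The best defence is that the text should govern and the code is only a sample. The SAP does not name weighted least squares; that is inferred from the response function. A log-linear model fitted by maximum likelihood would still give fitted proportions and a likelihood-ratio comparison with a main-effects model. This stands as a limit on the zero-variance argument, but it does not rescue the plan. Cells at 0% or 100% would still give unbounded individual parameters, and the large-sample approximations would be poor at these cell sizes.

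Three stronger readings are tempting, and the documents do not support them:

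- **The analysis is almost certain to be inestimable.** If every cell is occupied, the 16 proportions are still defined. What fails is the weighted fit, with its standard errors and tests. Only an empty cell removes the interaction itself, and that chance runs from 6% to 63% depending on the assumed preference shares.
- **A saturated model cannot address preference.** The stated aim is dependence on arm and preference, and randomisation to the preferred product is a contrast within the interaction. The fault is sparseness, not omission.
- **The question is left without an answer.** The planned contingency table gives a descriptive one. Its pooled matched/unmatched layout has only a 0% to 10% chance of a degenerate cell at compliance of 50% to 90%.

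The stakes are also low. The study tests no hypothesis (SAP 3.3.1), the section is exploratory, the table list in SAP 13.2 shows no output for this model, and changed analyses must be described in the CSR (SAP 1).

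**Conclusion.** The concern holds as a minor point. The text and the sample code specify different models, and the saturated fit that the code implies would usually lack valid standard errors and Wald tests.

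The probability of at least one degenerate or empty cell is about 90% at 50% compliance with equal preferences. It is 98% or more once compliance reaches 70% with preferences falling at random, and at least 99.6% at any compliance from 50% up once preferences are as uneven as 50/20/10/20. Milder unevenness (40/20/20/20) gives 96% to 97% at 50% to 60% compliance. The figure drops to 64% only with 50% compliance and evenly spread preferences.

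These figures rest on assumed compliance and preference rates, on 90 subjects, and on weighted least squares as the fitting method. No endpoint analysis is touched.

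**What to change.** Replace the model in SAP 9.6.2.1 with one pre-specified analysis:

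- **Model.** Firth-penalised logistic regression of compliance on randomised arm plus a three-level term (randomised to the preferred product, not randomised to it, no preference). Report odds ratios with 95% confidence intervals. Count IQOS as the preferred product for both IQOS arms.
- **Set.** All randomised subjects with a classifiable product-use category, not the AEECS.
- **Compliance.** Take actual arm as the Overall (V3 to V43) category of SAP 5.5.1.
- **Others.** State how this group is counted. SAP 5.5.1 places subjects with more than 50% missing product-use data there, and SAP 9.4 lists but does not analyse them.
- **Keep** the contingency table, and correct the log-linear wording.

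Collapsing the cells is not enough by itself: a saturated weighted fit to matched yes/no by four arms (8 cells) still meets a degenerate or empty cell in 40% to 99% of cases over compliance of 50% to 90%. Hence main effects only and a penalised likelihood.

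The cost is a few lines of SAP text and code. What is lost is the full preference-by-arm interaction, including separate effects of each stated preference, which 90 subjects cannot support.
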